8.5 Appendix 5: REACH-B Model

$$HCC \text{ risk} = 1 - P_0^{\exp(F)}, \text{ where}$$

$$F = (0.78798(\text{if male}) + 0.09859*(\text{age}) + 0.38823(\text{if } 15 \leq ALT < 44) + 0.96311(\text{if } ALT \geq 45) + 0.81308(\text{if HBeAg positive}) + 0.11648(\text{if } 300 \leq \text{HBV DNA} \leq 9999) + 1.31467(\text{if } 10^4 \leq \text{HBV DNA} \leq 10^5 - 1) + 2.27028(\text{if } 10^5 \leq \text{HBV DNA} \leq 10^6 - 1) + 2.09258(\text{if } \text{HBV DNA} \geq 10^6) - 6.12796$$

$P_0 = 0.99650$ if 5 –year HCC risk is estimated.

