The relationship between baseline variables or on-treatment variables and improvement of fibrosis will be analysis by univariate and multivariate logistic model. Univariate analysis will include gender, age, BMI category (< 25 or ≥ 25 kg/m²), baseline HBV DNA (≥ 2000 or < 2000 , IU/mL), baseline HBeAg sero-status, baseline ALT value, baseline LSM value, baseline total bilirubin, HBeAg loss at Week 24, treatment response at Week 24 and Week 48, ALT normalized or not at Week 24 and Week 48, change from baseline of LSM at Week 12 and Week 24, change from baseline of GGT at Week 24. Multivariate analysis will include sex, age and the factors with $P \leq 0.20$ in univariate analysis.

Proportion of LSM improvement will be summarized at Week48, Week96, Week144, Week192 and Week240 for patients with baseline LSM result in following groups: LSM improved (LSM decreased from baseline $\geq 30\%$), LSM stable (LSM decreased from baseline $< 30\%$ or no change from baseline), and LSM deteriorate (LSM increase from baseline).

Proportion of fibrosis stage improvement will be summarized at Week 48, Week 96, Week 144, Week 192 and Week 240 for patients of fibrosis stage measured by fibrosis improved from baseline, ≥ 2 stage fibrosis stage improved from baseline, ≥ 1 stage fibrosis stage, no change from baseline, fibrosis stage increase from baseline.

Analyses of correlation coefficients between LSM and ALT level will be analyzed by Pearson correlation coefficients and P-value during every 48 weeks by patients with ALT normal at baseline, patients with abnormal at baseline and overall.

Correlation coefficients between variables change at Week 12 and 24 and LSM change at Week 240 will be analyzed by correlation coefficients and P-value. The change from baseline of Gamma-Glutamyltransferase (GGT), Total Bilirubin (TBIL), Albumin (ALB), International Normalized Ratio (INR) and LSM will be included in the analysis of correlation coefficients at Week 12, platelets (PLT), GPR, APRI, FIB-4 and all the variables included at Week 12 will be included in the analysis of correlation coefficients at Week 24.

A 5-years predicted HCC risks by REACH-B model (see Section 8.5) and observed HCC risks (cumulative incidence of HCC) at Week 240 will be presented in table. Decline in LSM from baseline to Week 240 by visit will be analyzed by a line plot.

In addition, a listing of HBV DNA result will be provided for the following patients:

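### As printed, the REACH-B formula in SAP 8.5 gives no ALT term for values from 44 up to 45, so those subjects are scored like ALT below 15 and their predicted HCC risk is too low

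*SAP*

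**What the plan says.** SAP 8.5 (Appendix 5) defines predicted risk as 1 - P0^exp(F), with P0 = 0.99650 for the 5-year horizon. F is a sum of terms for sex, age, ALT band, HBeAg status and HBV DNA band, less 6.12796.

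ALT enters through two terms. The first adds 0.38823 for ALT from 15 to below 44; the second adds 0.96311 for ALT of 45 or more. The junction reads "ALT < 44) + 0.96311", and the upper condition reads "0.96311(\text{if } ALT \geq 45" (formula markup kept as extracted). ALT below 15 has no term and is the implicit reference.

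SAP 7.4.3 says where the formula is used: "A 5-years predicted HCC risks by REACH-B model (see Section 8.5) and observed HCC risks" are to be tabulated at Week 240. The list in SAP 9 names this output as Table 4.24.1. Neither section assigns an ALT between the two bands.

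**The concern.** The two ALT conditions do not meet. A value of 44, or a fraction such as 44.5, satisfies neither, so it contributes 0 to F, exactly as ALT below 15 does. The printed coefficients rise from 0 to 0.38823 to 0.96311 across the ALT bands, so a return to the reference value between the two higher bands cannot be intended.

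A programmer who codes the rule literally would under-predict HCC risk for every subject in that interval. The error has one direction, because omitting a positive term always lowers the prediction. ALT 44 is not a remote value in this cohort: inclusion criterion 3 admits subjects with or without ALT elevation, and exclusion criterion 2 removes only those above 10 times ULN. At stake is the accuracy of individual predictions in one exploratory table.

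**Working it through.** The documents state no predicted risk, so there is no sponsor figure to reproduce. The check evaluates the printed formula directly.

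**Inputs from SAP 8.5:** male 0.78798; age 0.09859 per year; ALT 0.38823 (15 <= ALT < 44) or 0.96311 (ALT >= 45); HBeAg positive 0.81308; HBV DNA 0.11648, 1.31467, 2.27028 or 2.09258 by band; constant -6.12796; P0 = 0.99650.

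**Assumed profile:** male, 45 years, HBeAg positive, HBV DNA 5x10^5 in the formula's unit, which Appendix 5 does not state.

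F without an ALT term = 0.78798 + 45 x 0.09859 + 0.81308 + 2.27028 - 6.12796 = 2.17993.

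| ALT | ALT term | F | Risk = 1 - 0.99650^exp(F) |
|---|---|---|---|
| 14 | 0 | 2.17993 | 3.05% |
| 43 | 0.38823 | 2.56816 | 4.47% |
| 44 (also 44.5) | 0 | 2.17993 | 3.05% |
| 45 | 0.96311 | 3.14304 | 7.80% |

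**Any profile.** Risk increases strictly with F, so the direction does not depend on the other covariates. The factor exp(F) at ALT 44 is exp(-0.38823) = 0.678 times its value at 43, and exp(-0.96311) = 0.382 times its value at 45. Risks for other assumed profiles:

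| Profile | ALT 14 | ALT 43 | ALT 44 | ALT 45 |
|---|---|---|---|---|
| Male, 60, HBeAg+, DNA 5x10^5 | 12.72% | 18.18% | 12.72% | 29.99% |
| Female, 40, HBeAg+, DNA 2x10^6 | 0.72% | 1.06% | 0.72% | 1.87% |
| Male, 45, HBeAg-, DNA 5x10^3 | 0.16% | 0.24% | 0.16% | 0.42% |

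**After closing the gap.** For the first profile, risk at ALT 44 becomes 4.47% if the middle band runs to below 45, or 7.80% if the upper band starts at 44.

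**How many subjects.** The documents give no ALT distribution. Assume log-normal ALT with median 35 to 60 and log-SD 0.4 to 0.9. The share in a one-unit interval centred on 44.5 is about phi(z)/(44.5 x SD), with z = ln(44.5/median)/SD:
- median 60, SD 0.9: 0.3775/40.05 = 0.9%;
- median 45, SD 0.4: 0.3988/17.8 = 2.2%.

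Of 186 subjects, that is about 2 to 4.

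**Shift in the cohort mean, first profile:**
- 44 joins the middle band: (2/186) x (4.47 - 3.05) = 0.015 points, to (4/186) x 1.42 = 0.03 points.
- 44 joins the upper band: (2/186) x (7.80 - 3.05) = 0.05 points, to (4/186) x 4.75 = 0.10 points.

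As an extreme, if all 4 had the 60-year-old profile, the shift would be (4/186) x (18.18 - 12.72) = 0.12 points, or (4/186) x (29.99 - 12.72) = 0.37 points. For scale, SAP 3.2.1 plans a margin of 3.4 points on the observed incidence.

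**The case against.** The strongest objection is that everything turns on one symbol. If the sponsor's page shows a less-or-equal sign before 44, no whole-number ALT is left out. The same formula opens a bracket after F that never closes, so either the source or its conversion is imperfect here. The two-sided HBV DNA bands all have closed upper limits, which fits a lost underline as well as a typing slip. This objection stands as a caveat. It does not remove the point entirely: with 44 included, values strictly between 44 and 45 would still have no band.

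A reader might infer that ALT is the only variable with a hole. That is true only for whole numbers. The HBV DNA bands stop at 9999, 10^5 - 1 and 10^6 - 1 and restart at the next integer, so a value such as 9999.5 also falls between bands.

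A reader might also take the drop in risk between ALT 43 and 44 as proof of error simply because risk is not monotone. That is too strong, since the printed HBV DNA coefficient itself falls from 2.27028 to 2.09258 at 10^6. The sound argument is narrower: ALT 44 falls back into the reference category.

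Finally, the documents do not reproduce the model's source, so they do not settle which band owns 44. They also do not show that the analysis program was written with the gap.

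**Conclusion.** The point holds for the formula as printed: ALT from 44 up to but not including 45 has no term, is scored as ALT below 15, and receives too low a predicted 5-year HCC risk. The understatement can be clear for an individual (3.05% instead of 4.47% or 7.80% in the first example) but is very small for the cohort: about 0.1 percentage points or less with that profile and 2 to 4 affected subjects. The subject count rests on an assumed ALT distribution, and the risks rest on assumed covariate profiles.

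A reader might infer that the predicted-against-observed comparison, or the HCC result itself, is unreliable. The documents do not support that. The formula enters only the exploratory Table 4.24.1, SAP 7.4.3 attaches no test to it, and neither primary endpoint uses it. This is a minor correction, worth making because it is cheap.

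**What to change.** Confirm the ALT limits against the model's source, then write bands that meet: most likely 15 <= ALT < 45 and ALT >= 45. Stating the limit as below 45, and not as up to and including 44, also covers fractional results.

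Write the HBV DNA bands the same way: 300 <= DNA < 10^4, 10^4 <= DNA < 10^5, 10^5 <= DNA < 10^6, and DNA >= 10^6.

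Add a programming check that each subject's ALT and HBV DNA fall in exactly one band, counting the reference band, and stop the run if any value does not.

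The cost is one character for the ALT limit, a few more for the HBV DNA limits, and one check in the program. No other analysis changes.

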9. MOCK TABLES, LISTINGS AND GRAPHS (TLGS)

Mock TLGs will be provided in a separate document.

TFL	Number	Title
Table	1.1	Disposition
Table	1.2	Major Protocol Deviations - mITT
Table	2.1.1	Demographics - mITT
Table	2.1.2	Baseline Characteristics - mITT
Table	3.1	Compliance and Duration of the Study Drug - mITT
Table	4.1.1	The Nominal Cumulative Incidence of Newly Diagnosed Hepatocellular Carcinoma (HCC) at Week 240 - mITT
Table	4.1.2	The Nominal Cumulative Incidence of Newly Diagnosed Hepatocellular Carcinoma (HCC) at Week 240 - PP
Table	4.1.3	The Cumulative Incidence of Newly Diagnosed Hepatocellular Carcinoma (HCC) - mITT
Table	4.1.4	The Cumulative Incidence of Newly Diagnosed Hepatocellular Carcinoma (HCC) - PP
Table	4.2.1	The Nominal Cumulative Incidence of Disease Progression at Week 240 - mITT
Table	4.2.2	The Nominal Cumulative Incidence of Disease Progression at Week 240 - PP
Table	4.2.3	The Cumulative Incidence of Disease Progression - mITT

Table	4.2.4	The Cumulative Incidence of Disease Progression - PP
Table	4.3.1	The Nominal Cumulative Incidence of Newly Diagnosed Hepatocellular Carcinoma (HCC) by Visit - mITT
Table	4.3.3	The Nominal Incidence of Newly Diagnosed Hepatocellular Carcinoma (HCC) by Visit - mITT
Table	4.4.1	The Nominal Cumulative Incidence of Disease Progression by Visit - mITT
Table	4.5.1	The Proportion of Subjects with Virological Response (Serum HBV DNA <20 IU/mL) by Visit - mITT
Table	4.5.1.1	The Proportion of Subjects with Virological Response (Serum HBV DNA <20 IU/mL) by Baseline HBeAg Status (HBeAg Positive and HBeAg Negative) by Visit - mITT
Table	4.5.1.2	The Proportion of Subjects with Virological Response (Serum HBV DNA <20 IU/mL) by Baseline HBV DNA Level (≥ 6 Log ₁₀ IU/mL and <6 Log ₁₀ IU/mL) by Visit - mITT
Table	4.5.3	The Proportion of Subjects with Virological Response (Serum HBV DNA <69 IU/mL) by Visit - mITT
Table	4.6.1	The Proportion of Subjects with ALT Normalization (Lab) at Week 48, 96, 144, 192 and 240 in Subjects Who Have Abnormal ALT at Baseline - mITT
Table	4.6.1.1	The Proportion of Subjects with ALT Normalization (AASLD Criteria) at Week 48, 96, 144, 192 and 240 in Subjects Who Have Abnormal ALT at Baseline - mITT
Table	4.7.1	The Proportion of Subjects Achieving HBeAg Loss, HBeAg Seroconversion, HBsAg Loss and HBsAg Seroconversion at Week 48, 96, 144, 192 and 240 for Subjects with Positive HBeAg at Baseline - mITT
Table	4.7.3	The Proportion of Subjects Achieving HBsAg Loss and HBsAg Seroconversion at Week 48, 96, 144, 192 and 240 for Subjects with Negative HBeAg at Baseline - mITT
Table	4.8.1	Change from Baseline for the log ₁₀ IU/mL in Serum HBV DNA by Visit - mITT
Table	4.9.1	Incidence of Subjects Who Experience Viral Breakthrough by Visit - mITT
Table	4.9.3	Incidence of Subjects With Unsatisfied Response by Visit - mITT
Table	4.10.1	The Proportion of Subjects with Histological Improvement - mITT
Table	4.11.1	The Proportion of Subjects with Cirrhosis Reversal - mITT

Table	4.12.1	The Mean Changes of Liver Stiffness Measurement by Visit - mITT
Table	4.12.3.1.1	Shift from Baseline in Fibrosis Stage for Patients with Baseline ALT > ULN - mITT
Table	4.12.3.2.1	Shift from Baseline in Fibrosis Stage for Patients with Baseline ALT ≤ ULN - mITT
Table	4.12.3.3	Shift from Baseline in Fibrosis Stage - mITT
Table	4.13.1	Incidence of TDF Resistance Substitutions - mITT
Table	4.14.1	The Relationship Between Baseline Variables or On-treatment Variables and Newly Diagnosed Hepatocellular Carcinoma (HCC) - mITT
Table	4.14.3	The Relationship Between Baseline Variables or On-treatment Variables and Disease Progression - mITT
Table	4.17.1	Cox Regression Analysis for Time to Newly Diagnosed Hepatocellular Carcinoma (HCC) - mITT
Table	4.17.3	Cox Regression Analysis for Time to Disease Progression - mITT
Table	4.18.1	Impact of HBV DNA and Virologic Response on Change of LSM - mITT
Table	4.18.3	The Mean Changes of Liver Stiffness Measurement by Visit for Patients with Advanced Fibrosis and Compensated Cirrhosis - mITT
Table	4.18.3.1	The % Changes of Liver Stiffness from baseline by Visit for Patients with Advanced Fibrosis and Compensated Cirrhosis - mITT
Table	4.19.7	Cox Regression Analysis for Time to Improvement of Fibrosis - mITT
Table	4.20.3	The Relationship Between Baseline Variables or On-treatment Variables and Improvement of Fibrosis - mITT
Table	4.21.1	Proportion of LSM Improvement - mITT
Table	4.21.3	Proportion of LSM Stage Improvement - mITT
Table	4.22.1	Analyses of correlation coefficients between LSM and ALT level - mITT
Table	4.23.1	Analyses of correlation coefficients between Variables Change at Week 12 and 24 and LSM Change at Week240 - mITT
Table	4.24.1	Predicted and Observed Risk of HCC at Week240 - mITT
Table	5.3.4	Mean values in Non-invasive fibrosis - SA
Table	5.1.1	Overall Summary of Adverse Events - SA
Table	5.1.2.1	All TEAEs by System Organ Class and Preferred Term - SA

Table	5.1.2.2	All Serious TEAEs by System Organ Class and Preferred Term - SA
Table	5.1.3.1	All TEAEs by Relationship to Study Drug – SA
Table	5.1.3.2	All Serious TEAEs by Relationship to Study Drug - SA
Table	5.1.4.1	All TEAEs by Intensity – SA
Table	5.1.4.2	All Serious TEAEs by Intensity - SA
Table	5.2	Change from Baseline in Vital Signs - SA
Table	5.3.1	Change from Baseline in Hematology - SA
Table	5.3.2	Change from Baseline in Blood Chemistry - SA
Table	5.3.3	Subjects with Treatment-emergent Laboratory Abnormalities - SA
Listing	1.1	Disposition – mITT
Listing	1.2	Analysis Set
Listing	1.3	Major Protocol Deviations - mITT
Listing	2.1.1	Demographics - mITT
Listing	2.1.2	Baseline Characteristics - mITT
Listing	2.2.1	Treatment History of Chronic Hepatitis B - mITT
Listing	2.3.1	Medical History - mITT
Listing	2.3.2	History of Treatment - mITT
Listing	2.3.3	Relevant Surgery - mITT
Listing	2.4	Inclusion and Exclusion Criteria - mITT
Listing	3.1.1	Prior Medications - mITT
Listing	3.1.2	Concomitant Medications - mITT
Listing	3.1.3	Non-Drug Therapies - mITT
Listing	3.2.2	Drug Accountability - mITT
Listing	3.3.1	Rescue Treatment - mITT
Listing	4.1	Newly Diagnosed Hepatocellular Carcinoma (HCC) and Disease Progression Events - mITT
Listing	4.2	HBV DNA - mITT
Listing	4.2.3	Listing of Subjects Mutation - mITT
Listing	4.3	Hepatitis B Five Item – mITT
Listing	4.4	Liver Stiffness Measurement – mITT
Listing	4.5	Childs-Pugh Score – mITT
Listing	5.1.1	Non-Serious Treatment-emergent Adverse Events - SA
Listing	5.1.2	Serious Treatment-emergent Adverse Events - SA
Listing	5.1.3	Treatment Related Treatment-emergent Adverse Events - SA
Listing	5.1.4	Treatment-emergent Adverse Events Leading to Permanent Discontinuation of Study Drug - SA
Listing	5.1.5	Treatment-emergent Adverse Events Leading to Permanent Discontinuation from the Study - SA

Listing	5.2	Vital Signs - SA
Listing	5.3.1	Hematology - SA
Listing	5.3.2	Blood Chemistry - SA
Listing	5.3.3	Blood Coagulation - SA
Listing	5.3.4	Urinalysis - SA
Listing	5.3.5	Pregnancy Test - SA
Listing	5.3.6	Alpha Fetoprotein (AFP) – SA
Listing	5.4	Physical Examination - SA
Listing	5.5	B-ULTRASOUND - SA
Figure	4.1.1	The Cumulative Incidence (95% CI) of Newly Diagnosed Hepatocellular Carcinoma (HCC) Over Time in Subjects - mITT
Figure	4.2.1	The Cumulative Incidence (95% CI) of Disease Progression Over Time - mITT
Figure	4.5.1	The Proportion (95% CI) of Subjects with HBV DNA <20 IU/mL Over Time - mITT
Figure	4.5.1.1	The Proportion (95% CI) of Subjects with HBV DNA <69 IU/mL Over Time - mITT
Figure	4.8.1.1	Mean HBV DNA Log10 IU/mL Over Time by Baseline ALT Significance - mITT
Figure	4.8.3	Distribution of HBV DNA levels Over Time - mITT
Figure	4.15.1	Kaplan-Meier Curves for Newly Diagnosed Hepatocellular Carcinoma (HCC) – mITT
Figure	4.15.1.1.1	Kaplan-Meier Curves for Newly Diagnosed Hepatocellular Carcinoma (HCC) in Subjects with Platelets <100 - mITT
Figure	4.15.1.1.2	Kaplan-Meier Curves for Newly Diagnosed Hepatocellular Carcinoma (HCC) in Subjects with Platelets >=100 - mITT
Figure	4.15.3	Kaplan-Meier Curves for Disease Progression – mITT
Figure	4.15.3.1.1	Kaplan-Meier Curves for Disease Progression in Subjects with Platelets <100 - mITT
Figure	4.15.3.1.2	Kaplan-Meier Curves for Disease Progression in Subjects with Platelets >=100 - mITT
Figure	4.18.3.1	Decline in LSM from baseline to Week 240 - mITT
Figure	5.3.1.1	Mean Estimated Glomerular Filtration Rate Over Time by Baseline eGFR - SA
Figure	5.3.1.2	Mean Creatinine Clearance Rate Over Time by Baseline Ccr - SA
Figure	5.3.2	Mean Serum Phosphorus Over Time - SA
Figure	6.1.1	Change of Average LSM/ALT By Visit - mITT
Figure	6.1.2	Change of Average LSM By Visit - mITT
Figure	6.1.3	Change of Median of LSM By Visit - mITT

GlaxoSmithKline (China) Investment Co., Ltd.
Protocol 201213

Version: 2.0
Feb 26, 2021

Figure	6.3.1	Change of Average GPR APRI FIB-4 By Visit - mITT
Figure	6.3.2	Change of Median of GPR APRI FIB-4 By Visit - mITT
Figure	6.4.1	Change of Fibrosis Stage By Visit - mITT
